- 1) Patients with treated CNS metastases are eligible if they are symptomatically stable while off steroid therapy for a minimum of 7 days
- 2) Symptomatic leptomeningeal disease. Patients with asymptomatic treated or untreated leptomeningeal disease could be enrolled provided that all other protocol-defined criteria are met.
- 3) Patient who are receiving any other investigational agents
- 4) Major surgical procedure, other than for diagnosis, within 4 weeks prior to initiation of study treatment, or anticipation of need for a major surgical procedure during the study
- 5) Diagnosis of another malignancy. However, patients with prior or concurrent malignancy whose natural history or treatment does not have the potential to interfere with the safety or efficacy assessment of the investigational regimen are eligible for this trial.
- 6) Evidence of pleural and/or pericardial effusion. A small and/or asymptomatic effusion is not exclusionary.
- 7) Any other disease, metabolic dysfunction, physical examination finding, or clinical laboratory finding that, in the view of the investigator, contraindicates the use of an investigational drug, may affect the interpretation of the results, or may render the patient at high risk from treatment complications.
- 8) Pregnancy or breastfeeding, or intention of becoming pregnant during study treatment or within 6 months after the final dose of study treatment.

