4.2.2.1 MGC018

MGC018 will be administered by IV infusion at a dose of 2.0 mg/kg on Day 1 of each 28-day cycle until completion of cycle 8, unacceptable toxicity, or loss of clinical benefit as determined by the investigator after an integrated assessment of radiographic and biochemical data, local biopsy results (if available), and clinical status (see Section 3.1.1 for details). For subjects weighing ≥ 100 kg the doses will be based on 100 kg for these subjects. To decrease the frequency and severity of palmar-plantar erythrodysesthesia (PPE) and effusions, prednisone 40 mg will be given twice daily for three days of each cycle starting the evening after each infusion for a total of 6 doses. In addition, patients will be provided with a strong or moderate-strength topical steroid cream to be applied as prescribed to the hands and soles prophylactically for the first 12 weeks of therapy.

Administration of MGC018 will be performed in a monitored setting where there is immediate access to trained personnel and adequate equipment and medicine to manage potentially serious reactions. For anaphylaxis precautions, see Appendix 3. MGC018 infusions will be administered per the instructions outlined in Table 3.

Table 3. Administration of first and subsequent MGC018 infusions

| Study Drug | First Infusion | Subsequent Infusions |
|-----------------|---|--|
| MGC018 infusion | 
Premedication with acetaminophen (650mg to 1000 mg), diphenhydramine 50 mg PO or IV, famotidine 40 mg PO or 20 mg IV, and corticosteroid (e.g | 
If the patient experienced an infusion-related reaction (IRR) with any previous infusion, additional premedication may also be considered. |

| | | |
|---|---|---|

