5. ASSESSMENT OF SAFETY

5.1 SAFETY PLAN

The safety plan for patients in this study is based on clinical experience with MGC018 in completed and ongoing studies.

Measures will be taken to ensure the safety of patients participating in this study, including the use of stringent inclusion and exclusion criteria and close monitoring of patients during the study.

Administration of all study therapies will be performed in a monitored setting in which there is immediate access to trained personnel and adequate equipment and medicine to manage potentially serious reactions. Guidelines for managing patients who experience anticipated adverse events, including criteria for treatment interruption or discontinuation, are provided in Section 4.2.3.

Refer to Sections 5.2–5.6 for details on safety reporting (e.g., adverse events, pregnancies) for this study.

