5.1.1 Risks associated with MGC018

MGC 018 has been associated with risks such as the following: infusion-related reactions, pneumonitis, myelosuppression, peripheral edema, severe cutaneous adverse reactions, pericardial effusion, pleural effusion, ocular toxicity, arthritis, and colitis. Please refer to the MGC018 IB for a detailed description of anticipated safety risks for MGC018.

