5.2.3 Adverse events of special interest (AESIs)

AESIs are a subset of events to monitor of scientific and medical concern specific to the product, for which ongoing monitoring and rapid communication by the Investigator to the study sponsor is required (no more than 24 hours after learning of the event). Such an event might require further investigation in order to characterize and understand it. Depending on the nature of the event, rapid communication by the trial sponsor to other parties (e.g., Regulatory Authorities; MacroGenics) may also be warranted.

AESIs for this study include the following:

- Cases of potential drug-induced liver injury that include an elevated ALT or AST in combination with either an elevated bilirubin or clinical jaundice, as defined by Hy's law:
Treatment-emergent ALT or AST $> 3 \times$ ULN in combination with total bilirubin $> 2 \times$ ULN
Treatment-emergent ALT or AST $> 3 \times$ ULN in combination with clinical jaundice
- Grade 3 or higher pneumonitis
- Grade 3 or higher pleural and/or pericardial effusion
- Grade 3 or higher ocular toxicities (e.g., uveitis, retinitis, optic neuritis)
- Severe cutaneous reactions (e.g., Stevens-Johnson syndrome, dermatitis bullous, toxic epidermal necrolysis)

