Appendix 1 Study Flowcharts

Table 1: Screening Procedural Outline

| Procedure | Screening Visit (D-28 to D1) | Notes |
|--------------------------------|---------------------------------|--|
| Eligibility Assessments | | |
| Informed Consent | X | Must be documented before any study-specific screening procedures are performed, and may be obtained >28 days prior to treatment initiation |
| Inclusion/Exclusion Criteria | X | |
| Medical History | X | |
| Demographic Data | X | |
| Baseline Assessments | | |
| Con Medication Review | X | Medication (e.g., prescription drugs, over-the-counter drugs, vaccines, herbal or homeopathic remedies, nutritional supplements) used by a patient in addition to protocol-mandated treatment from 7 days prior to initiation of study treatment until the treatment discontinuation visit |
| Vital Signs | X | Includes: temperature, heart rate, respiratory rate, blood pressure |
| Weight | X | |
| Height | X | |
| Physical Exam | X | Includes evaluation of the head, eyes, ears, nose, and throat, and the cardiovascular, dermatological, musculoskeletal, respiratory, gastrointestinal, and neurological systems. Record abnormalities observed at baseline in the patient's medical records |
| ECOG Performance Status | X | |

| | | |
|----------------------------------|---|--|
| Laboratory Tests ^a | X | CBC with differential, serum chemistry (bicarbonate/total carbon dioxide, sodium, potassium, chloride, glucose, BUN, creatinine, total protein, albumin, phosphorus, calcium, total bilirubin, alkaline phosphatase, ALT, AST), thyroid function (TSH, free/total T3, free T4) |
| Pregnancy Test | X | Serum pregnancy test at screening for women of child-bearing potential only ^b |
| Tumor Biopsy ^c | X | Mandatory for study entry |
| Imaging Assessments ^d | X | CT (preferred) or MRI with contrast (unless contraindicated) of chest, abdomen and pelvis MRI (preferred) or CT of head with contrast (unless contraindicated) to assess for presence of CNS metastases |

^aScreening laboratory test results must be obtained within 14 days of treatment initiation. Screening labs that are performed outside the 14-day window for eligibility criteria may be repeated on C1D1, prior to treatment, to verify the subject continues to meet eligibility requirements.

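### Exclusion 6 lets a patient with a symptomatic pleural or pericardial effusion start full-dose MGC018 as long as the effusion is called small

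*Combined protocol and SAP*

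**What the plan says.** The criterion is item 6 of the exclusion list (4.1.2 in the table of contents, headed ii in the body). Its first sentence excludes patients with "Evidence of pleural and/or pericardial effusion". Its second reads "A small and/or asymptomatic effusion is not exclusionary". Neither size nor symptoms are defined, and no other eligibility criterion deals with effusion specifically. Item 7 lets the investigator keep out a patient with any other condition that "may render the patient at high risk from treatment complications".

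Other sections treat effusion as a hazard of this drug:

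- Section 5.1.1 includes in its list of risks "pericardial effusion, pleural effusion, ocular toxicity, arthritis, and colitis".
- Section 5.2.3 names as an adverse event of special interest "Grade 3 or higher pleural and/or pericardial effusion".
- Section 4.2.2.1 mandates prednisone 40 mg twice daily for three days of each cycle, with the stated aim "To decrease the frequency and severity of palmar-plantar erythrodysesthesia (PPE) and effusions".
- Tables 14 (pleural) and 15 (pericardial) in section 4.2.3.2 require a hold at grade 2 or 3. The drug resumes one dose level lower if the effusion resolves to grade 1 or less within 21 days. Grade 4 means permanent discontinuation.
- Section 5.1 gives among its safety measures "including the use of stringent inclusion and exclusion criteria and close monitoring of patients during the study".

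**The concern.** The word pair joining the two properties in item 6 makes each one sufficient. A symptomatic effusion therefore escapes the exclusion once someone calls it small. With no definition of small, the local investigator and the central office that confirms eligibility have no common threshold, and similar patients at different sites could be handled differently.

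What is at stake is patient safety at entry and consistency between sections. Section 5.1 relies on strict entry criteria as a safety measure. For one of the drug's listed risks, the criterion lets in a patient who already has the problem with symptoms, at the full starting dose. No statistical operating characteristic is involved.

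**Working it through.** The plan gives no figure on this point, so the check is a reading of the sentence followed by a comparison of sections.

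**Step 1. What the sentence admits.** Classify effusions by size (small, more than small) and symptoms (no, yes), which gives 2 × 2 = 4 types. The present rule exempts an effusion if it is small OR asymptomatic. The proposed rule exempts it if it is asymptomatic AND needs no intervention.

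| Effusion at screening | Present item 6 | Proposed wording |
|---|---|---|
| Small, no symptoms | admitted | admitted unless intervention is indicated |
| Small, symptoms | **admitted** | **excluded** |
| More than small, no symptoms | admitted | admitted unless intervention is indicated |
| More than small, symptoms | excluded | excluded |

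The present wording admits 3 of 4 types and excludes 1. The proposed wording always excludes both symptomatic types. It also excludes an asymptomatic effusion for which drainage or other treatment is indicated. These are counts of types, not of patients.

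**Step 2. The same effusion before and during treatment.** Take a small effusion with symptoms that would be graded 2.

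- At screening, item 6 exempts it and the patient may start at level 1, 2.0 mg/kg (Table 4).
- Arising on treatment, Table 14 or 15 stops the drug. If the effusion resolves to grade 1 or less within 21 days, dosing resumes one level lower, at 1.5 mg/kg for a patient who was on 2.0 mg/kg.
- Tables 14 and 15 concern suspected MGC018-related toxicity. Under section 5.3.1.3 a pre-existing condition is reported as an adverse event only if it worsens. A baseline effusion that stays the same would therefore not become a reportable event, and nothing in the tables clearly applies to it.

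**Step 3. Assumption on grading.** The protocol grades by CTCAE v5.0 but does not reproduce its effusion criteria. The general scale in section 5.3.1.5, for events not listed in CTCAE, allows mild symptoms within grade 1. If every small symptomatic effusion would be graded 1, there is no mismatch with Tables 14 and 15, and the argument rests on sections 5.1, 5.1.1, 5.2.3 and 4.2.2.1. If every one would be grade 2 or 3, all are mismatched. The truth lies between these limits, and the documents do not fix where.

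**Step 4. Does another provision close the gap?**

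- Item 7 is discretionary, is worded for other conditions, and sets no effusion limit.
- The central eligibility review (section 4.6.2) applies the same criteria, including item 6 as written.
- The pre-dose check (section 4.4) requires an acceptable clinical assessment but gives no effusion threshold.

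**Step 5. Statistical design.** The rule (stop at 0 of 9, reject at 3 or more of 17) does not involve item 6. The probability of rejection is the sum over x = 1 to 9 of P(X1 = x) × P(X2 ≥ max(0, 3 − x)), with X1 binomial(9, p) and X2 binomial(8, p). It equals 0.0466 at p = 0.05 and 0.8122 at p = 0.25. These reproduce the stated 4.7% and 81.2%, and rewording the criterion leaves them unchanged.

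**The case against.** The strongest reply is that entry is broad by design. ECOG 0 to 2 and any number of prior therapies are allowed. Items 1 and 2 of the same list turn on symptoms: treated CNS metastases are acceptable if symptomatically stable off steroids, and asymptomatic leptomeningeal disease is acceptable even untreated. A symptom-based effusion rule fits that pattern.

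This stands for asymptomatic effusions. A reader might infer that admitting a large asymptomatic effusion is also an error. The documents do not support that: symptom-based entry is consistent with items 1 and 2 and may be intended. The same argument does not help the small symptomatic effusion. Item 2 excludes symptomatic disease, whereas item 6 admits it on size alone.

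The second reply is that other safeguards limit the consequence: central confirmation of eligibility, assessment before each dose, chest CT at every tumor assessment, prednisone each cycle, and the hold rules. This stands in part. They reduce the likely harm, but none sets an entry limit.

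The third reply is that harm is inferred. This also stands. A reader might infer that MGC018 worsens an existing effusion, or that a baseline effusion raises the risk of a severe one. The protocol lists effusion as a risk but says neither. It refers to the Investigator's Brochure for detail, and that is not available here.

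**Conclusion.** The concern holds for symptomatic effusions. As written, item 6 makes a symptomatic pleural or pericardial effusion eligible for full-dose treatment if it is called small, and this is out of line with the protocol's own handling of effusion. The reading of the sentence is secure. The mismatch with Tables 14 and 15 assumes that at least some of these effusions would be graded 2 or higher.

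The severity is minor. One of four types of effusion is admitted without an evident rationale, and the number of such patients is unknown. There is no effect on N = 17, type I error or power. Whether asymptomatic effusions should have an upper size limit, pericardial ones in particular, is a question to put to the sponsor and is not counted here as an error.

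**What to change.** Replace both sentences of item 6 with:

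> *Pleural or pericardial effusion that is symptomatic or for which drainage or other intervention is indicated (i.e. above grade 1). An asymptomatic effusion needing no intervention is not exclusionary.*

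This removes the undefined word small and uses a test that the investigator and the central office can apply to the same records. It depends on symptoms and need for treatment, so it does not cap size. If the sponsor wants a cap for asymptomatic effusions, it needs a stated measurement. Before adopting the words in parentheses, the sponsor should check them against the CTCAE v5.0 effusion grades. If mild symptoms can be grade 1, drop the parenthesis and keep the symptom test. Tables 14 and 15 need no change.

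The cost is one amended criterion. No new procedure is needed, because screening already requires "CT (preferred) or MRI with contrast (unless contraindicated) of chest, abdomen and pelvis" together with a history and physical examination. The downside is that a few patients now eligible would be excluded, or delayed until the effusion is treated. That could slightly slow the expected accrual of 1 to 2 patients per month, by an amount the documents do not allow one to estimate.

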4.2 STUDY TREATMENT

The investigational medicinal product (IMP) for this study is MGC018.

4.2.1 Study treatment formulation, packaging, and handling

4.2.1.1 MGC018

MGC018 will be supplied by MacroGenics as sterile liquid at a nominal protein concentration of 10 mg/mL in a single-use glass vial containing 93 mg/9.3mL MGC018. The drug product is formulated in a solution of 0.46 mg/mL L-histidine, 1.47 mg/mL L-histidine hydrochloride monohydrate, 90 mg/mL sucrose, and 0.1 mg/mL polysorbate 80, pH 5.7. For further information on the MGC018 formulation, refer to the MGC018 investigator's brochure (IB).

4.2.2 Study treatment dosage, administration, and compliance

The treatment regimens are summarized in Section 3.1.1.

Any overdose or incorrect administration of MGC018 should be noted in the patient's medical records and reported according to Sections 5.4 and 5.5. Adverse events associated with an overdose or incorrect administration of any of the study treatments should be recorded in the patient's medical records and appropriate eCRF.

Guidelines for dosage modification, treatment interruption or discontinuation for patients who experience adverse events are provided in Section 4.3.3 and Appendix 4. Dose modification of all study drugs (MGC018) will not be permitted.

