3.3 RATIONALE FOR STUDY DESIGN

3.3.1 Rationale for MGC018 dose and schedule

MGC018 will be administered at a dose of 2.0 mg/kg every 28 days continuously until completion of 8 cycles, disease progression, or unacceptable toxicity. The dose was selected on the basis of available clinical pharmacokinetics, efficacy, and safety data from the open label, dose escalation CP-MGC018-01 phase I study. Specifically, the dosing was 3.0 mg/kg every 21 days in the prior phase 1 dose escalation study of MGC018 (Shenderov et al. 2021). However, there has been subsequent evidence of increased neutropenia and hand-foot syndrome at this dose, and doses of 2.0 mg/kg every 28 days and 2.7 mg/kg every 28 days are being investigated in the phase 2 and 3 MGC018 trials. For patients who require a dose-reduction, the first reduction would be to 1.5 mg/kg every 28 days and a second reduction to 1.0 mg/kg as needed. Please refer to the MGC018 IB for details.

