- When several toxicities with different grades of severity occur at the same time, appropriate action should be made according to the highest grade observed.
- If, in the opinion of the investigator, a toxicity is considered to be due solely to MGC018 and is of sufficient grade to warrant treatment delay, therapy should be delayed and omitted until resolution of toxicity.
- If, in the opinion of the investigator, a toxicity attributed to MGC018 is of sufficient grade to warrant permanent discontinuation of therapy, therapy should be permanently discontinued.

For patients who require a dose-reduction, the first reduction would be to 1.5 mg/kg every 28 days with a second reduction to 1.0 mg/kg every 28 days, as needed (**Table 4**).

Table 4. Dose levels of MGC018

| Dose levels | MGC018 |
|-------------------------|---------------|
| Level 1 (starting dose) | 2.0 mg/kg Q4W |
| Level -1 | 1.5 mg/kg Q4W |
| Level -2 | 1.0 mg/kg Q4W |

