4.2.3.2 Guidelines for management of suspected MGC018-related toxicities

Criteria for treatment modification and guidelines for the management of toxicities are summarized below. Generally, temporary suspension of MGC018 must occur if a patient experiences a serious adverse event or a grade 3 or 4 non-serious adverse event assessed by the investigator as related to MGC018. If the event resolves to grade ≤ 1 , MGC018 may be restarted at the same dose level. If MGC018 is delayed due to toxicity for > 8 weeks beyond when the next dose should have been given, the patient must be permanently discontinued from MGC018.

PULMONARY EVENTS

Immune-mediated pulmonary events are a potential risk with MGC018. Patients will be assessed for pulmonary signs and symptoms throughout the study and will have computed tomography (CT) scans of the chest performed at every tumor assessment.

All pulmonary events should be thoroughly evaluated for other commonly reported etiologies such as pneumonia or other infection, lymphangitic carcinomatosis, pulmonary embolism, heart failure, chronic obstructive pulmonary disease, or pulmonary hypertension. Management guidelines for pulmonary events are provided in Table 5.

Table 5. Management Guidelines for Pneumonitis

| Event | Management |
|--------------|---|
| Grade 1 | 
 • Continue MGC018 and monitor closely. • Re-evaluate on serial imaging. • No specific therapy required |
| Grade 2 | 
 • Hold MGC018 • Consider treatment with corticosteroids equivalent to 1–2 mg/kg/day oral prednisone or equivalent divided twice daily • Taper corticosteroids over 4 weeks or as clinically indicated • Resume MGC018 administration at next scheduled dose if pneumonitis resolves to grade 1 or baseline within 5 days with or without treatment. On resuming MGC018, reduce dose by one dose level. • Discontinue MGC018 after second occurrence |
| Grade 3 or 4 | 
 • Permanently discontinue MGC018 • Hospitalize • Referral for pulmonary consult with diagnostic evaluation with chest X-ray and CT scan. • Initiate treatment with IV corticosteroids, suggest methylprednisolone at 2 to 4 mg/kg/day divided twice daily. Higher doses may be used in consultation with the sponsor's medical monitor. • If event does not improve within 3 to 5 days after initiating corticosteroids, consider adding an immunomodulatory agent. |

HEPATIC EVENTS

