For palmar-plantar erythrodysesthesia, hold MGC018 until toxicity resolves to \leq grade 1. MGC018 may be resumed with MGC018 decrease of one dose level. Discontinue MGC018 if patient does not recover to \leq grade 1 within 28 days.

Table 9. Management Guidelines for Dermatologic Events

| Event | Management |
|-------|------------|
|-------|------------|

| | |
|-----------------------------|---|
| Dermatologic event, Grade 1 | 
 • For dry skin, consider application of moisturizers as needed to affected area • Symptomatic treatment with low dose topical corticosteroids (betamethasone 0.1% or hydrocortisone 1%) or antihistamines • Persistent grade 1 or 2 rash should be managed with higher dose topical corticosteroids and/or oral prednisone (1 to 2 mg/kg/day) if there is not improvement with topical therapies or the rash is associated with other dermal toxicities such as pruritis. • Evaluate for use of concomitant medications and herbal supplements that may exacerbate skin toxicity. |
| Dermatologic event, Grade 2 | 
 • Treat as grade 1 • No dose reduction required after first occurrence • On resuming MGC018, reduce dose by one dose level after second and third occurrences • Discontinue MGC018 after fourth occurrence |
| Dermatologic event, Grade 3 | 
 • Hold MGC018 • Initiate oral corticosteroids (oral prednisone 1 to 2 mg/kg/day) • Evaluate participant use of concomitant medications and herbal supplements that may exacerbate skin toxicity • Consider obtaining skin biopsy if SJS or TEN is suspected. If possible, refer to specialized care center for clinical management. Cyclosporine and/or IV immunoglobulin may be considered for management of SJS or TEN. • Resume MGC018 at next scheduled dose if: • Skin toxicity resolves to \leq grade 1 or baseline within 21 days with maximal supportive care • Discontinue study drugs if skin toxicity does not resolve to \leq grade 1 or baseline within 21 days, or for any grade SJS or TEN of any duration. • On resuming MGC018, reduce dose by one dose level after first and second occurrences • Discontinue MGC018 after third occurrence |

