| Neutropenia, Grade 1 or 2 | 
 • No specific therapy required • MGC018 should not be given to participants with neutrophil counts ≤ 1500 cells/mm³ • Consider dose reduction of MGC018 |
| Neutropenia, Grade 3 | 
 • Hold MGC018 until recovery to \leq grade 1 • Monitor neutrophil counts weekly until recovery to \leq grade 1 • Discontinue MGC018 if not recovered to \leq grade 1, within 21 days • Restart MGC018 if recovered to \leq grade 1 within 21 days. • On resuming MGC018, reduce dose by one dose level after first and second occurrences • Discontinue MGC018 after third occurrence |
| Neutropenia, Grade 4 | 
 • Hold MGC018 until recovery to \leq grade 1 • Monitor neutrophil counts weekly until recovery to \leq grade 1 • Discontinue MGC018 if not recovered to \leq grade 1, within 21 days • Restart MGC018 at one or two level dose reduction if recovered to \leq grade 1 within 21 days. • On resuming MGC018 reduce dose by two dose levels after first occurrence • Discontinue MGC018 after second occurrence |
| Thrombocytopenia, Grade 1 | 
 • No specific therapy required • Consider dose reduction of MGC018 |

| | |
|-----------------------------------|--|
| Thrombocytopenia, Grade 2 or 3 | 
 • Hold MGC018 until recovery to \leq grade 1 • Monitor platelet counts weekly until recovery to \leq grade 1 • Restart MGC018 with one level dose reduction if recovered to \leq grade 1 • Reduce dose by one dose level on resumption after second and third occurrences • Discontinue MGC018 after fourth occurrence • Discontinue MGC018 if not recovered to \leq grade 1 within 21 days. |
| Thrombocytopenia, Grade 4 | 
 • Hold MGC018 until recovery to \leq grade 1 • Monitor platelet counts weekly until recovery to \leq grade 1 • Restart MGC018 with one or two level dose reduction if recovered to \leq grade 1 • Discontinue MGC018 if not recovered to \leq grade 1 within 21 days. • On resuming MGC018 reduce dose by two dose levels after first occurrence • Discontinue MGC018 after second occurrence |
| Anemia, Grade 1 | 
 • No specific therapy required |
| Anemia, Grade 2 | 
 • Consider iron replacement therapy, erythropoiesis stimulating agent |

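### Section 4.2.2 forbids MGC018 dose modification and points to text that does not exist, while Section 4.2.3, Table 4 and 12 of the 15 toxicity tables direct dose reductions

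*Combined protocol and SAP*

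**What the plan says.** Section 4.2.2 (study treatment dosage, administration, and compliance) tells the reader that guidelines for modifying, interrupting or discontinuing treatment after adverse events "are provided in Section 4.3.3 and Appendix 4". The next sentence reads "Dose modification of all study drugs (MGC018) will not be permitted". It carries no exception.

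Other sections direct the opposite:

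- Section 3.3.1, on patients who need a reduction: "the first reduction would be to 1.5 mg/kg every 28 days and a second reduction to 1.0 mg/kg as needed".
- Section 4.2.3.1, introducing Table 4: "For patients who require a dose-reduction, the first reduction would be to 1.5 mg/kg every 28 days". Table 4 lists 2.0, 1.5 and 1.0 mg/kg every four weeks as Levels 1, -1 and -2.
- Section 4.2.3.2, on palmar-plantar erythrodysesthesia after recovery: "MGC018 may be resumed with MGC018 decrease of one dose level".
- Section 4.2.3.2, Table 13, Grade 3 neutropenia: "On resuming MGC018, reduce dose by one dose level after first and second occurrences". Several other tables use the same line.

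The opening of Section 4.2.3.2 also has a general rule. After a suspension for a serious or Grade 3 or 4 related event that has resolved to Grade 1 or better, "MGC018 may be restarted at the same dose level".

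**The concern.** The dosing section and the toxicity section give opposite instructions on what dose to give after a toxicity. The sentence before the prohibition names modification, interruption and discontinuation as three separate actions, and the prohibition names only the first. Read literally, a site may hold or stop MGC018 but may resume it only at 2.0 mg/kg.

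Two things are at stake. One is the patient's dose: a literal reader would either give the full dose again where a table calls for a lower one, or stop a drug that the table would continue at a lower dose. The other is compliance: a table-directed reduction breaches Section 4.2.2, and a full-dose restart breaches the table. Section 9.2 requires deviations to be documented and does not allow prospective requests to deviate, so the text should not put a site in that position. The pointer that should settle the question leads nowhere.

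**Working it through.** **1. Does the pointer resolve?** Section 4.3 is concomitant therapy, and its only subsection is 4.3.1. The list of appendices ends at Appendix 3, and so does the body. That list survives in the public copy, so removed pages do not explain the gap. The guidelines are in Section 4.2.3. Section 5.1 names that section for adverse event management, although its sentence mentions interruption and discontinuation and not dose modification.

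**2. How widely do the tables contradict the prohibition?** Body numbering is used, because the front-matter list of tables is numbered differently. The toxicity tables are 5 to 19, so 19 - 5 + 1 = 15.

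| Tables | Direct a dose-level reduction? |
|---|---|
| 5 pneumonitis, 6 transaminases, 7 bilirubin, 8 diarrhea or colitis, 9 dermatologic, 10 nephritis, 11 endocrine (hyperthyroidism), 12 blepharitis, 13 hematologic, 14 pleural effusion, 15 pericardial effusion, 18 musculoskeletal | Yes: 12 |
| 16 nervous system, 17 cardiovascular, 19 infusion-related reactions | No: 3 |

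The palmar-plantar erythrodysesthesia rule stands in the text outside the tables and adds one more reduction.

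**3. One event, read both ways.** Take Grade 3 neutropenia that recovers to Grade 1 or better within 21 days.

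| Occurrence | Table 13 with Table 4 | Section 4.2.2 read literally |
|---|---|---|
| First | Resume at 1.5 mg/kg | Resume at 2.0 mg/kg, or stop |
| Second | Resume at 1.0 mg/kg | Resume at 2.0 mg/kg, or stop |
| Third | Discontinue | (no dose question arises) |

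**4. Size of the dose difference.** The inputs are the Table 4 levels. The ratio is the starting dose divided by the directed dose.

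- Against Level -1: 2.0 / 1.5 = 1.33
- Against Level -2: 2.0 / 1.0 = 2.0

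**5. Does it reach the statistical design?** Sections 3.1.3 and 6.4 give a Simon two-stage rule: stop if there is no response in 9 patients, otherwise continue to 17 and reject at 3 or more responses. The probability of rejection is the sum over x = 1 to 9 of P(X1 = x) × P(X2 ≥ 3 - x), with X1 binomial on 9 patients and X2 binomial on 8.

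- At a 5% response rate: 0.0466 (plan: 4.7%)
- At a 25% response rate: 0.8122 (plan: 81.2%)

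Both figures reproduce. No dose rule enters the calculation, so they stand whichever dosing sentence governs.

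**The case against.** The strongest reply is that nobody would follow the prohibition. The sentence just before it says that guidelines for dosage modification exist, so the paragraph contradicts itself and signals an error. Section 4.2.3 is devoted to dose modification and follows closely, Table 4 names the levels, and each table row states its own reduction. The reference to all study drugs for a single-drug trial looks like leftover text. A site in doubt can ask the coordinating office (Sections 4.6.1 and 4.6.4). All of this stands. It makes harm unlikely and limits the rating, but it does not make the sentence correct.

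A reader might infer that the affected toxicities are known to be frequent here, because Section 3.3.1 says "there has been subsequent evidence of increased neutropenia and hand-foot syndrome at this dose". That dose was 3.0 mg/kg every 21 days. This trial starts at 2.0 mg/kg every 28 days and adds prednisone and topical steroid prophylaxis (Section 4.2.2.1). The documents do not show how often these events occur at this dose.

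A reader might also treat the number of contradicting tables as a measure of risk. It shows only how often the text repeats the reduction rule. Some of those reductions are conditional: Grade 2 blepharitis reduces only if symptoms lasted more than 14 days, and after Grade 3 diarrhea a restart is considered only when colitis is excluded and another cause is found.

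The same-dose restart in Section 4.2.3.2 is introduced as a general rule and is permissive, so it already reads as a default that a specific table overrides. A precedence line there is therefore optional.

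**Conclusion.** The inconsistency is real and can be shown from the text alone. Section 4.2.2 prohibits what Section 3.3.1, Section 4.2.3.1 with Table 4, the palmar-plantar erythrodysesthesia rule and 12 of 15 toxicity tables direct, and its cross-reference points to a section and an appendix that do not exist. For a patient dosed under the literal reading, the restart dose would be 1.33 or 2.0 times the directed one, or treatment would end early.

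Two stronger conclusions are not supported. One is that the trial adopted a no-reduction design: the rest of the document shows that reductions are intended. The other is that patients will be overdosed: this would need a site to follow one sentence against everything around it, and without usable event rates the number affected cannot be estimated. Sample size, type I error and power are untouched.

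This is a should-fix wording correction to a safety rule. The dose ratios assume that the prohibition concerns the dose level and leaves holds and discontinuations available, as the three separate actions in the preceding sentence indicate.

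**What to change.** In Section 4.2.2:

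- Delete the sentence that prohibits dose modification.
- Replace the reference to Section 4.3.3 and Appendix 4 with a reference to Section 4.2.3 and Table 4. Specify the Table 4 in Section 4.2.3.1, because Appendix 1 also contains a Table 4 (the PK and ADA calendar).

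Optionally, add one line to Section 4.2.3.2 saying that the event-specific tables override the general same-dose restart.

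The cost is a wording amendment with the approvals that Section 9.3 requires. No new clinical decision is needed, because Table 4 and the event tables already set the reductions. Sample size, error rates, visits and data collection stay as they are.
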